STUDY PROTOCOL AND STATISTICAL ANALYSIS

Official Title: Effectiveness of Transcranial Magnetic Stimulation on Dysphagia in Patients with Parkinson's Disease: A Randomized Double-Blind Study

Unique Protocol Id: E-70198063

Date: 22.10.2025

Our study included patients aged 40-75 years with a diagnosis of Parkinson's disease who were followed up at the Physical Medicine and Rehabilitation and Neurology outpatient clinics and who experienced dysphagia symptoms. Inclusion criteria included being followed up with a diagnosis of Parkinson's disease, moderate to severe Parkinson's disease (Hoehn-Yahr 2-4), patients describing dysphagia symptoms, and being able to give informed consent. Exclusion criteria included intracranial metallic devices, cardiac pacemakers, history of seizures, antipsychotic use, diagnosis of depression, diagnosis of dementia, findings of additional neurological disease (intracranial lesion on imaging, hydrocephalus, positive Babinski sign, cerebellar signs), and normal FEES evaluation.

A total of 129 patients followed up with a diagnosis of Parkinson's disease from the Physical Medicine and Rehabilitation and Neurology outpatient clinics were screened based on their files. Forty-one patients who met the inclusion criteria were interviewed. Six patients declined to participate in the study. Six patients experiencing dysphagia symptoms had normal FEES results. The remaining 29 patients were included in the study. After randomization, there were 14 participants in the 5 Hz group and 15 participants in the 10 Hz group. During the treatment process, one patient from the 5 Hz group and two patients from the 10 Hz group withdrew from the study for personal reasons. Thirteen patients from each group participated in the post-treatment and 9-month follow-up evaluations. The relevant study flow chart is shown in Figure 1.

Patient files were scanned through the hospital system, and patients who met the inclusion criteria for the study were contacted by telephone. During this conversation, patients were informed about the content, purpose, duration, and possible complications of the study. Patients who agreed to participate in the study were invited for an examination. During this examination, patients were assessed for the presence of exclusion criteria. For patients deemed suitable for participation, the swallowing assessment form, FOIS, FSS, and EAT-10 test were completed. This was followed by a flexible endoscopic swallowing evaluation (FEES). During this evaluation, the YALE-2016 valeric residue scale, YALE-2016 piriform sinus residue scale, and penetration aspiration scale were scored. Participants were then assigned to one of two treatment groups.

Randomization was performed using a computer program. Treatments were administered at 5 Hz to one group and 10 Hz to the other group. Treatments consisted of a total of 10 sessions over two weeks, applied bilaterally to the pharyngeal and mylohyoid cortex by another researcher. Neither the researchers performing the assessments nor the patients were aware of

the treatment group. The TMS device used in our clinic was the Magstim Rapid 2 (Magstim Co Ltd, [name]), and a butterfly coil (D70) was used for stimulation. All treatment parameters except frequency were kept the same in both treatment groups. rTMS treatment was administered with a pulse duration of 10 seconds, an interval of 25 seconds, a total of 2000 pulses, and a stimulation intensity of 90% of the RMT of the first dorsal interosseous muscle of the hand. The current literature was reviewed when determining the treatment stimulation point. Studies conducted with stroke patients showed that 4-6 cm lateral and 2-4 cm anterior to the vertex were used for mylohyoid cortex stimulation. (17-20) The study referenced by all these studies is the one conducted by Khedr et al., in which the cortical topography of the swallowing muscles was mapped. (21) In our study, the vertex point was determined according to the international 10-20 method. Subsequently, based on the existing literature, 6 cm lateral and 3 cm anterior to the vertex point was determined as the mylohyoid and pharyngeal cortex stimulation point. Both groups were given cervical strengthening, shaker, massako exercises, and triflo breathing exercises as home exercises. After 10 sessions of rTMS treatment, the patients underwent a second evaluation, and the scores from the first evaluation were used.

After rTMS treatment, patients were asked to continue swallowing exercises. They were called for a follow-up evaluation at 9 months. The same evaluations performed at the first and second visits were also performed at the third visit.

G-Power software was used to calculate the sample size. According to the ANOVA analysis, the significance value was $p<0.05$; the effect size was 0.30, and the minimum sample size was calculated as 26 at a 95% confidence interval.

The statistical analysis of the study was performed using IBM SPSS Statistics version 27.0 and R analysis version 4.5.0. Descriptive statistical methods were used to examine demographic data. The normality of data distribution was assessed using the Shapiro-Wilk test. Since the data were found to be non-normally distributed, non-parametric tests were used.

The “Cochran test” and “Brunner Langer test” were used to evaluate the time-dependent distribution of categorical data within groups, and the “Dunn Bonferroni test” was used for pairwise comparisons of significant data. The “Chi-square test” was used for the intergroup evaluation of categorical data. The Friedman test was used to evaluate the time-dependent change in numerical data within groups, and the Mann-Whitney U test was used for the intergroup evaluation. The correlation of pre-treatment parameters was evaluated using Spearman correlation analysis.

The statistical significance level was set at $p<0.05$.

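### The title promises a randomised test of whether TMS works, but the only randomised contrast is 5 Hz versus 10 Hz, with the same exercises in both arms

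*Combined protocol and SAP*

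**What the plan says.** The Official Title opens with "Effectiveness of Transcranial Magnetic Stimulation on Dysphagia" and ends by calling the trial, in Parkinson's disease, randomised and double-blind. The document has no separate objective or hypothesis, so the title is its only statement of the question.

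The procedures text describes the allocation: "Participants were then assigned to one of two treatment groups", and then "Treatments were administered at 5 Hz to one group and 10 Hz to the other group". The treatment description adds that "All treatment parameters except frequency were kept the same in both treatment groups" and that "Both groups were given cervical strengthening, shaker, massako exercises, and triflo breathing exercises as home exercises". The exercises do not stop with the stimulation: "After rTMS treatment, patients were asked to continue swallowing exercises". The next evaluation is at 9 months.

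The closing statistical paragraph plans two kinds of analysis:

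- **Within each group over time:** "The Friedman test was used to evaluate the time-dependent change in numerical data within groups". The Cochran and Brunner-Langer tests do the same for categorical data.
- **Between the two groups:** Mann-Whitney for numerical data and chi-square for categorical data.

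**The concern.** A title that joins effectiveness of TMS to a randomised double-blind design tells the reader that the effect of TMS was compared, under randomisation, with its absence. No such comparison exists here. The only planned analyses that could speak to effectiveness are the within-group tests, and neither randomisation nor blinding protects them.

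Two misreadings are at stake. A significant change within an arm could be taken as randomised, blinded evidence that rTMS improves swallowing. A non-significant difference between 5 Hz and 10 Hz, with both arms improving, could be taken to mean that both frequencies work, when it fits equally well with neither working.

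**Working it through.** **1. Title against design.**

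| Element | What the document provides |
|---|---|
| Question in the title | Effectiveness of TMS; no comparator named |
| Randomised groups | 14 patients at 5 Hz, 15 at 10 Hz (29 in all) |
| Group without active stimulation | None described |
| Stated difference between arms | Frequency only |
| Co-intervention | Same home exercises in both arms, continued after rTMS |
| Evaluated after treatment and at 9 months | 13 per arm |

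All 29 randomised patients are allocated to active rTMS, so randomisation identifies only the difference between frequencies.

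**2. What a within-group change contains.** Besides any rTMS effect, it contains:

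- **Exercise**, prescribed to everyone and continued to the 9-month visit. The text gives no start date for it.
- **Expectation.** Blinding conceals the frequency, not the fact of being stimulated. This matters most for patient-reported scores such as the EAT-10.
- **Disease course** over 9 months, with no untreated comparison.
- **Regression to the mean**, because a normal FEES was an exclusion and the same examination supplied the baseline residue and penetration-aspiration scores.

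**3. Size of the regression to the mean.** From the patient flow, 41 interviewed less 6 who declined leaves 35. Six of these had a normal FEES, leaving 29. Assume that one normally distributed score drives selection and that the lowest 6/35 = 0.171 is cut off.

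- The cut-off is at z = -0.949, where the normal density is 0.254.
- The baseline mean of those retained rises by 0.254 / (1 - 0.171) = 0.31 SD.
- The expected later fall is (1 - correlation) × 0.31, which is 0.15 SD at correlation 0.5 and 0.09 SD at 0.7.

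The effect is real but modest, and it applies directly only to the FEES variable used for selection.

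**4. How often a within-arm test is significant when rTMS does nothing.** The simulation used 13 patients, 3 visits, equicorrelated normal scores, a common shift at visits 2 and 3 from causes other than rTMS, and a Friedman test at 0.05. The range in each row spans correlation 0.5 to 0.7.

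| Common shift (assumed) | Significant within-arm tests |
|---|---|
| 0 SD | about 5% |
| 0.2 SD | 9% to 11% |
| 0.4 SD | 21% to 31% |
| 0.6 SD | 41% to 65% |
| 0.8 SD | 67% to 87% |

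A repeat run agreed within about two percentage points. With no shift the test holds its 5% level. Everything above that is the test correctly detecting a change that is not due to rTMS. The regression effect in step 3 is smaller than 0.2 SD, so on its own it would not move the test beyond that row.

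**5. What a null frequency comparison could mean.** The sample-size statement gives an effect size of 0.30 for an ANOVA. If this is Cohen's f with two equal groups, it equals a standardised difference d = 2 × 0.30 = 0.60. At 13 per arm and a single visit, power to detect that is about 0.33 (normal approximation). Power of 80% needs d = (1.960 + 0.842) × √(2/13) = 1.10. A non-significant result is therefore likely even if the frequencies differ moderately, and it says nothing about either frequency against no stimulation.

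**The case against.** The strongest reply is that the harm is predicted, not documented. The document contains no conclusion and no claim of efficacy. Its body is open about the two frequencies and plans between-group tests, so nobody who reads it in full would suppose that there was a sham arm. On this view a title that omits its comparator is a reporting weakness and not an analysis error. That is right about the body, but the title is the only statement of the question, and it claims a property that the design lacks.

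The reply also limits four inferences that a reader might draw:

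- **That a false signal for TMS is likely.** Taking only the 0.6 or 0.8 SD rows would suggest this, but no shift of that size has a source in the documents. The range starts at 5%.
- **That selecting on abnormal FEES explains any improvement.** At 0.09 to 0.15 SD, regression to the mean is at most about a quarter of a 0.6 SD shift.
- **That the trial is invalid without a sham arm.** The frequency comparison is a legitimate randomised question, and before-after change may still be described.
- **That a group-by-visit test can now be made confirmatory.** The statistical paragraph names no such test. The text reports completed 9-month evaluations and normality already assessed, so a test chosen now would be post hoc.

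**Conclusion.** The point holds as a mismatch between the stated question and the design. By randomised comparison, the trial can answer only whether 5 Hz and 10 Hz rTMS differ when both are added to home exercises. Within-group change cannot be attributed to rTMS. This follows from the arms and the co-intervention alone and needs no simulation.

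How often the within-group tests would mislead cannot be fixed from the documents. It runs from about 5% to 87% per arm for common shifts of 0 to 0.8 SD, assuming equicorrelated normal scores and correlations of 0.5 to 0.7. The documents do not show that a claim of efficacy has been made from these tests. The finding is that the title invites one.

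**What to change.** - **Title and reports.** Retitle the study, and word any objective or conclusion in its reports, as a comparison of 5 Hz with 10 Hz rTMS, both added to home swallowing exercises.
- **Basis of the conclusion.** Rest it on the between-group comparison.
- **Within-group results.** Report the Friedman, Cochran and Brunner-Langer results as uncontrolled and descriptive, and say that they cannot be attributed to rTMS.
- **Null result.** State that finding no difference between frequencies is not evidence that both work.
- **If a group-by-visit comparison of change is added,** record it as an addition to the SAP and label it post hoc, because the data are already collected.

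No new arm and no new data are needed. The first four changes cost only wording, and the optional fifth is a small analysis addition. The downside is a more modest headline claim.

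### Do equal pulses at 5 Hz and 10 Hz undermine the claim that the two arms differ only in frequency?

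*Combined protocol and SAP*

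**What the plan says.** The document has no numbered sections. The relevant text is in the paragraphs on randomisation and treatment.

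- **Contrast:** "Treatments were administered at 5 Hz to one group and 10 Hz to the other group".
- **Delivery:** "Treatments consisted of a total of 10 sessions over two weeks, applied bilaterally to the pharyngeal and mylohyoid cortex by another researcher".
- **Blinding:** "Neither the researchers performing the assessments nor the patients were aware of" the assigned arm.
- **Matching:** "All treatment parameters except frequency were kept the same in both treatment groups".
- **Settings, given once for both arms:** "rTMS treatment was administered with a pulse duration of 10 seconds, an interval of 25 seconds, a total of 2000 pulses", with intensity at 90% RMT.

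The document does not give the number of trains, pulses per train, stimulation time or session length for either arm. It does not define what lasts 10 s, or say whether the 2000 pulses are per session, per hemisphere or for the whole course.

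**The concern.** Frequency is the trial's only contrast: both arms are active and there is no sham arm. The matching sentence tells the reader that nothing else differed. Frequency, train length, train count and total pulses are tied together by arithmetic, however, so the first cannot change while the other three all stay fixed. If train length, interval and pulses are held equal, the 5 Hz arm must receive more trains over a longer session.

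On that view, a difference between arms, or the lack of one, could reflect train count, pulses per train, stimulation time or session length as well as frequency. The sentence would then invite a narrower causal reading than the design supports. A visibly longer session in one arm might also be thought to threaten patient blinding.

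**Working it through.** **Inputs from the treatment paragraphs:** frequencies 5 and 10 Hz; 10 s duration; 25 s interval; 2000 pulses; 10 sessions; both sides treated.

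**Assumptions:** 10 s is the train length (a single magnetic pulse cannot sensibly last 10 s), and 25 s is the gap between trains. Time common to both arms, such as moving the coil, is left out at first.

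**Step 1. Reproduce the stated total.** Pulses per train = frequency × train length; trains = 2000 ÷ pulses per train.

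- 5 Hz: 5 × 10 = 50 per train; 2000 ÷ 50 = 40 trains; 40 × 50 = 2000.
- 10 Hz: 10 × 10 = 100 per train; 2000 ÷ 100 = 20 trains; 20 × 100 = 2000.

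The stated total reproduces in both arms, so the listed settings are mutually consistent.

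**Step 2. Stimulation time.** Trains × 10 s gives 400 s against 200 s. Equivalently, pulses ÷ frequency gives 2000 ÷ 5 = 400 s and 2000 ÷ 10 = 200 s. The second form contains no train length or interval: the doubling comes from the frequency alone.

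**Step 3. Length of the stimulation sequence.** Run time = trains × 10 + (trains − 1) × 25.

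| Reading of 2000 | 5 Hz | 10 Hz | Ratio |
|---|---|---|---|
| One run per session | 40×10 + 39×25 = 1375 s | 20×10 + 19×25 = 675 s | 2.04 |
| Per hemisphere per session | 2×1375 = 2750 s | 2×675 = 1350 s | 2.04 |
| Per session, 1000 per side | 2×(20×10 + 19×25) = 1350 s | 2×(10×10 + 9×25) = 650 s | 2.08 |
| Whole course, 200 per session in one run | 4×10 + 3×25 = 115 s | 2×10 + 25 = 45 s | 2.56 |
| Whole course, 100 per side per session | 2×(2×10 + 25) = 90 s | 2×10 = 20 s | 4.5 |

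The last two rows imply sessions of 20 to 115 s and are the least plausible. If the 25 s runs from train start to train start, one run takes 39×25 + 10 = 985 s against 19×25 + 10 = 485 s, a ratio of 2.03. In the one-run case the gap is 1375 − 675 = 700 s (11.7 min) per session.

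**Step 4. Does the session last at least twice as long?** Add a common time c to both arms.

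- One run: (1375 + c)/(675 + c) = 2 gives c = 25 s.
- 1000 per side: (1350 + c)/(650 + c) = 2 gives c = 50 s.

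Beyond those values the ratio is below 2. For 1000 per side, assumed changeovers of 1, 2 and 5 min give 1410/710 = 1.99, 1470/770 = 1.91 and 1650/950 = 1.74. The document gives no changeover time, but it describes treatment of both sides with one coil, so some common time is likely.

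**Step 5. Could another design have matched everything?**

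- Equal train counts with 10 s trains: pulses become 1000 v 2000 (20 trains) or 2000 v 4000 (40 trains).
- Equal train counts and equal pulses: train length becomes 20 s v 10 s (20 trains) or 10 s v 5 s (40 trains).

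Every version leaves something other than frequency unequal. Holding total pulses fixed is one defensible choice among these.

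**The case for a change.** The strongest case for a change is this. The sentence claims that everything apart from frequency was matched, and Step 5 shows that this cannot be literally true under any arrangement. Train count and session length are ordinary features of a stimulation regimen, and the document never says that they differed. Because the 2000 has no stated unit although treatment covered two sides and ten sessions, a reader cannot recover the delivered dose or session length. Rewording costs one sentence, and a difference that cannot be avoided is a reason to disclose it.

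Part of this stands. The sentence is too broad, and the missing unit and undefined 10 s make exact replication harder.

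The step from there to a fault in the plan does not stand.

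- The settings follow directly after the sentence, and the ordinary reading is that these programmed settings were the ones matched. They can be.
- Train counts and stimulation times follow from those settings by arithmetic, so an informed reader can work them out, given the train-length reading.
- The document reports no result and makes no statement crediting an effect to frequency alone. The worry concerns how a later report might be worded.
- On blinding, each patient experiences only one session length, someone other than the assessors gives the treatment, and nothing indicates that patients or assessors were told what length to expect. The point is speculative and carries no weight here.

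**Conclusion.** No change to the plan is called for. With 10 s read as train length, the arms differ two-fold in trains (40 v 20) and in stimulation time (400 v 200 s). The stimulation sequence is about twice as long at 5 Hz (1375 v 675 s as one run per session), and the ratio for the whole session is lower once common time is counted. At equal pulses, the two-fold stimulation time is part of what comparing 5 Hz with 10 Hz means.

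The randomised comparison of the two regimens as delivered is not biased by this. The planned between-group tests (Mann-Whitney U and chi-square) do not use train count or session length, and neither does the sample-size statement. The study is described in the past tense, so treatment delivery is already fixed.

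What is left is loose wording and missing descriptive detail. The sponsor can settle from treatment records what the 10 s and the 2000 refer to and reconcile the broad sentence with the settings beneath it; this review proposes no setting. Analysts and readers can meanwhile treat the contrast as two regimens matched on the listed settings. Doing so changes no number, test or conclusion in the document.

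### The three pairwise visit comparisons use Bonferroni; Holm's step-down on the same p-values keeps the family-wise guarantee and adds a little power

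*Combined protocol and SAP*

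**What the plan says.** The Combined protocol and SAP has no numbered sections. Its closing paragraphs on statistical analysis name the Cochran and Brunner-Langer tests, which "were used to evaluate the time-dependent distribution of categorical data within groups". A Dunn-Bonferroni test then "was used for pairwise comparisons of significant data", which reads as pairwise testing only after a significant overall result. For numerical outcomes, "The Friedman test was used to evaluate the time-dependent change in numerical data within groups"; no pairwise test is named in that sentence. The significance level is 0.05, with sidedness not stated.

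There are three visits: baseline, after the ten sessions, and 9 months. The treatment and follow-up paragraphs say that "The same evaluations performed at the first and second visits were also performed at the third visit". On numbers, the participant paragraph says "Thirteen patients from each group participated in the post-treatment and 9-month follow-up evaluations". The Bonferroni factor is not written out, but three visits give three pairs and so a factor of three. No reason is given for choosing Bonferroni over a step-down method.

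**The concern.** Baseline v post-treatment and baseline v 9 months are the comparisons that show whether swallowing changed within a group and whether the change lasted. With 13 patients per group their power is modest. Bonferroni holds all three pairs to the threshold needed when all three nulls are true, even after one pair has been shown to differ. That gives up power for no gain in the stated guarantee. At stake are missed within-group changes, including outcomes where the overall test is significant but no pair is. False positives are not the problem: the plan's rule errs on the cautious side.

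**Working it through.** **Inputs.** From the document: alpha 0.05 (two-sided assumed), 13 patients per group, 3 visits, effect size 0.30, total sample size 26. Assumed, because the document gives no values: mean shifts, correlations between visits, and number of scale levels.

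**1. The plan's own figure.** The sample-size paragraph says that "the effect size was 0.30, and the minimum sample size was calculated as 26 at a 95% confidence interval". Power, correlation and type of ANOVA are not stated. For a repeated-measures ANOVA with 2 groups and 3 visits, the noncentrality is N × f² × m / (1 − ρ).
- N = 26, ρ = 0.5: 26 × 0.09 × 3 / 0.5 = 14.04. On 2 and 48 degrees of freedom the power is 0.912.
- N = 24: 24 × 0.09 × 3 / 0.5 = 12.96. On 2 and 44 degrees of freedom the power is 0.886.

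So 26 is reproduced at 90% power with ρ = 0.5 (also at 95% power with ρ = 0.6). It was sized for an overall test, not for pairs.

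**2. What each rule demands.** Without ties, Dunn's standard error for a difference in mean ranks is √[k(k+1)/(6n)] = √(12/78) = 0.392.

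| Rule | p needed | \|z\| needed | Mean-rank difference |
|---|---|---|---|
| Bonferroni, every pair | 0.05/3 | 2.39 | 0.94 |
| Holm, smallest p | 0.05/3 | 2.39 | 0.94 |
| Holm, second p | 0.05/2 | 2.24 | 0.88 |
| Holm, third p | 0.05 | 1.96 | 0.77 |

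**3. Why Holm costs nothing.** Holm multiplies the ordered p-values by 3, 2 and 1, where Bonferroni uses 3, 3 and 3, so every Bonferroni rejection is also a Holm rejection. If t of the three nulls are true, the first true null that Holm reaches is tested at no more than 0.05/t. The chance of any false rejection is then at most t × 0.05/t = 0.05. This is the Bonferroni guarantee, and like Bonferroni's it presumes that each pairwise p-value is valid.

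**4. Size of the gain.** The simulations used 20,000 to 40,000 arms per setting, n = 13 and three visits. With shifts of 0.4-0.8 SD and correlations of 0.2-0.9, Holm adds about 1-7 points for truly different pairs. With 0.8 SD at both later visits, correlation 0.5 and continuous scores, power for baseline v post-treatment rises from 40% to 44%. Holm's family-wise error stayed below 5% in every setting run.

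**5. Ties.** On coarse scales the choice of standard error matters more than Holm. Power for baseline v post-treatment under the plan's Bonferroni rule (0.8 SD at both later visits):

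| Scores, correlation | SE ignoring ties | Tie-corrected SE | Difference |
|---|---|---|---|
| 5-level, 0.5 | 23% | 43% | 20 points |
| 5-level, 0.7 | 34% | 62% | 28 points |
| 8-level, 0.7 | 49% | 67% | 18 points |

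The document does not say which is used. For three visits the tie-corrected standard error is √[Σ(rank − 2)²]/n, summed over all patients and visits. Without ties each patient contributes 2, giving √26/13 = 0.392 as above.

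**6. Dropping the factor of three.** With three visits, two equal pairs imply that all three are equal. A valid 5% overall test followed by valid unadjusted 5% pairs is therefore a closed test. At f = 0.30, a (0, d, d) pattern has SD of means d√2/3, so d = 0.636 SD. At ρ = 0.5, power for baseline v post-treatment would rise from 25% to 37%, or from 36% to 44% if half the gain is lost by 9 months.

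Closure needs each pairwise test to be valid on its own, and Dunn's z uses one pooled standard error. Take baseline equal to 9 months, a 0.6 SD post-treatment shift and continuous scores. The false-positive rate for baseline v 9 months is:

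| Correlation baseline-post / pairs with 9 months | Overall test, no adjustment | With Bonferroni |
|---|---|---|
| 0.9 / 0.4 | 8.2% | 2.3% |
| 0.9 / 0.2 | 9.3% | 2.9% |

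Milder imbalance (0.8 / 0.5) stays near 5%, at most 5.4%.

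**The case against.** **The stronger reading.** A reader might infer that, with exactly three visits, the preliminary overall test already controls the error, so the Bonferroni factor is redundant and should go. The closure logic is right, but the document does not supply what it needs. It names Dunn's test and gives no correlations. Its visits are unevenly spaced: a two-week course separates the first two, and the third is at 9 months. Step 6 shows what can then go wrong. With all visits equal, the overall test itself reached 5.7% (continuous scores, 0.9/0.4) and 7.0% (binary, 0.9/0.2).

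A reader might also put the cost of Bonferroni at 20-30 points. On 5- and 8-level scores, gains of that size from dropping the factor appear only when Dunn's standard error ignores ties; with the correction they shrink to about 12-14 points. Nor is the plan doubly penalised: in simulated data without ties, every Bonferroni-significant Dunn pair also passed the Friedman test, so the rule behaves as ordinary Bonferroni.

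**What else can be said for the plan.**
- It is valid, and Bonferroni is a defensible preference. That stands; the point is an improvement, not an error.
- The study is complete and the data have been examined, so any more liberal rule is a late change. That stands and calls for disclosure.
- Bonferroni is the only multiplicity adjustment named, while several scales are tested in two groups. True, but Bonferroni over three visits does not address that either, and Holm keeps the same protection for the visits.
- The Dunn-Bonferroni wording sits with the categorical outcomes. Its application after Friedman is therefore an inference, although Holm works with any pairwise test. Brunner-Langer was not simulated.

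**Conclusion.** The point holds as a modest, low-cost improvement. The planned rule is valid and somewhat wasteful, and Holm is never less powerful. The 1-7 point gain depends on the assumed shifts and correlations, since the document gives only an effect size of 0.30.

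Removing the adjustment altogether would gain about 4-20 points with tie correction. It is acceptable only with pairwise tests valid on their own two visits, such as Wilcoxon signed-rank or exact McNemar, and not with pooled-variance Dunn z.

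One limit applies to Holm as well. With Dunn's pooled z under unequal correlations, its control below 5% is a simulation result for the settings run, not a theorem. Holm has less slack than Bonferroni at its later steps, so more uneven correlations should not be presumed covered.

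**What to change.** In the statistical analysis paragraphs, replace Bonferroni with Holm for the three pairwise visit comparisons within each outcome and group. State that Dunn's z uses a tie-corrected standard error on the ordinal scales, and name the pairwise test that follows Friedman. Suggested text: *Where the overall three-visit test is significant, the three pairwise p-values will be adjusted by Holm's method; Dunn's z will use a standard error corrected for ties.*

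If the team wants the larger gain of the closed procedure, it should use Wilcoxon signed-rank or exact McNemar for the pairs. It would then report each adjusted p-value as the larger of the overall and the pairwise p, and say that this relies on there being exactly three visits.

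Report Bonferroni and Holm p-values side by side and disclose that the change was made after the data were examined. The cost is a sentence or two and one more column of p-values; no new patients, data or software are needed. Multiplicity across scales and groups needs its own statement.

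### Chi-square for between-arm categorical data probably discards the order of some ordered variables; at 13 per arm that costs power against a one-directional shift, and the plan's own Mann-Whitney test avoids it

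*Combined protocol and SAP*

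**What the plan says.** The statistical analysis paragraphs at the end of the combined protocol and SAP sort the data into two classes.

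- **Categorical.** Cochran's test and Brunner-Langer "were used to evaluate the time-dependent distribution of categorical data within groups". Between arms, chi-square "was used for the intergroup evaluation of categorical data". No trend, ordinal or exact version is named.
- **Numerical.** Within arms: "The Friedman test was used to evaluate the time-dependent change in numerical data within groups". For the comparison of 5 Hz with 10 Hz, the plan states that "the Mann-Whitney U test was used for the intergroup evaluation".

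The plan assigns no variable to either class. The assessment paragraph lists what was measured: "the swallowing assessment form, FOIS, FSS, and EAT-10 test were completed", followed by endoscopy, at which the two residue scales were rated ("piriform sinus residue scale, and penetration aspiration scale were scored"). That makes six scales and one swallowing form whose content is not described. On follow-up the document says: "The same evaluations performed at the first and second visits were also performed at the third visit". The participant paragraph gives 13 patients per arm at both later visits.

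**The concern.** Cochran's test handles repeated two-level data. Brunner-Langer is a rank-based longitudinal method, and its natural use is with ordered data. Numerical data already have Friedman as their within-arm rank test. The obvious reason to list Brunner-Langer under categorical data is therefore that the class holds ordered variables with three or more levels. If so, the plan uses their order within arms and discards it between arms.

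The 5 Hz v 10 Hz comparison is the only randomised contrast in the trial. Chi-square spreads a one-directional shift over several degrees of freedom, so with 13 per arm a real shift is more often reported as no difference than it would be under the rank test the plan uses for numerical data.

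**Working it through.** **Inputs from the documents.** 13 per arm (participant paragraph); significance level 0.05 (statistical analysis, taken as two-sided); chi-square for categorical and Mann-Whitney for numerical data between arms; effect size 0.30 and minimum sample size 26 (sample-size paragraph).

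**Assumptions, not in the documents.** 3, 5 or 8 levels, equally likely in the reference arm; a proportional-odds shift with odds ratio (OR) 3 or 4.5; uncorrected Pearson chi-square.

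**The plan's own figure.** Read as a repeated-measures ANOVA with 2 groups, 3 visits, correlation 0.5 and power 0.90 (the last four assumed), the noncentrality is λ = f²·N·m/(1 − ρ) = 0.09 × 26 × 3 / 0.5 = 14.04. On 2 and 48 degrees of freedom this gives power 0.912, so 26 is reproduced. The point made here does not depend on it.

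**Choice of shift.** If 0.30 is read as a two-group Cohen's f, then d = 2f = 0.6 and OR = exp(0.6 × π/√3) ≈ exp(1.088) ≈ 3. OR 4.5 shows a larger effect.

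**One table by hand.** Suppose the arms are 4/4/3/1/1 and 1/2/3/3/4 over five ordered levels.

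- Chi-square with equal arms is Σ(a − b)²/(a + b) = 9/5 + 4/6 + 0/6 + 4/4 + 9/5 = 5.27 on 4 df, p = 0.26.
- Mann-Whitney: the midranks are 3, 8.5, 14.5, 19.5 and 24. The first arm's rank sum is 12 + 34 + 43.5 + 19.5 + 24 = 133, against an expected 13 × 27/2 = 175.5. The tie-corrected variance is (169/12) × (27 − 720/650) = 364.7, so z = −42.5/19.10 = −2.23 and p = 0.026 (exact 0.028).

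**Power by simulation.** The second arm follows logit P(Y ≤ j) = logit P_ref(Y ≤ j) − ln(OR). With five levels and OR 4.5, this moves 0.2 at each level to 0.053/0.076/0.121/0.221/0.529. There were 40,000 simulated trials per setting at OR 3 and 200,000 at OR 4.5. Repeat runs agreed to within about 1 point.

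| Levels | OR 3: chi-square v Mann-Whitney | OR 4.5: chi-square v Mann-Whitney | OR 4.5: only Mann-Whitney / only chi-square significant | No effect: rejection rate, chi-square v Mann-Whitney |
|---|---|---|---|---|
| 3 | 23 v 30% | 38 v 49% | 14 / 3% | 5.3 v 5.0% |
| 5 | 16 v 32% | 28 v 53% | 27 / 2% | 4.0 v 4.8% |
| 8 | 9 v 33% | 18 v 54% | 38 / 1% | 2.4 v 4.9% |

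**How much of the gap is lost order.** The last column shows chi-square becoming conservative as tables thin out. With 26 patients on three or more levels, some level holds at most 8, so its expected count per arm is at most 4; sparse tables are unavoidable. Exact versions of both tests put them on an equal footing (1,500 trials per setting, standard error about 1.2 to 1.3 points). At OR 4.5 this gives 34 v 44% at 3 levels and 33 v 51% at 5 levels. The gaps are 10 and 18 points, against 11 and 25 in the table.

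**Where the advantage disappears.**

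- Two levels, OR 4.5: 45 v 40% with the large-sample tests. The exact tests coincide at 30%.
- Three levels, one nearly empty (0.02/0.49/0.49), OR 3: 27 v 26%. Over 150 random three-level baselines, Mann-Whitney had more power in 141 under proportional odds and in 139 under a normal shift; the reversals inspected had one nearly empty level. At 4, 5 and 8 levels it had more power in 150 of 150 under both.
- Pure spread difference (0.1/0.2/0.4/0.2/0.1 v 0.3/0.15/0.1/0.15/0.3): 39 v 7%, in favour of chi-square.

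**The case against.** The strongest objection is to the premise: no named scale is shown to be in the categorical class. Four features point to numerical handling. Friedman is applied to numerical data over time, and the only measures the documents describe as repeated are the form and the six scales, so some of these must be numerical and already go to Mann-Whitney. The data are checked with Shapiro-Wilk. The sample size comes from an ANOVA. The treatment paragraph speaks of scores ("the patients underwent a second evaluation, and the scores from the first evaluation were used"). In addition, Brunner-Langer can be run on two-level data, and the undescribed form could itself hold the ordered items, so that none of the six scales is affected.

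Most of this stands. A reader might infer that the six swallowing scales were all compared by chi-square, or that any reported lack of difference between arms is an artefact of the test. The documents support neither. They do support the narrower inference, because a rank method placed beside Cochran's test has little purpose if every categorical variable has two levels or no order.

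It is also fair that part of the power gap is conservatism rather than lost order, that OR 4.5 has no anchor in the plan, and that 13 per arm is the larger limit: at OR 3, Mann-Whitney itself misses about two-thirds of real shifts. These points reduce the size of the loss. They do not reverse its direction for a shift on a well-populated ordered scale.

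**Conclusion.** The concern holds conditionally. The plan's wording suggests that one or more ordered variables with at least three levels, whether scales or form items, are compared between arms by a test that ignores order. For such a variable under a one-directional shift, chi-square gives up about 7 to 11 points of power at 3 levels, 16 to 25 at 5 and 24 to 36 at 8, over OR 3 to 4.5. With exact tests at OR 4.5, the gap is about 10 points at 3 levels and 18 at 5. These figures rest on assumed level counts, equally likely reference levels and proportional odds.

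For any scale already tested by Mann-Whitney, nothing changes. There is no reliable gain for two-level variables or for a three-level variable with a nearly empty level, and Mann-Whitney does worse on a pure spread difference. The change is worth making because the better test is already in the plan. Confidence is medium, since only the sponsor can say which variables are affected.

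**What to change.** State for each scale and each form item whether it is nominal, binary, ordered or numerical. Compare every ordered variable with three or more levels between arms by the Mann-Whitney test already named, tie-corrected and preferably exact. Keep chi-square for nominal or binary variables.

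The cost is a short addition to the SAP and a re-run on collected data in SPSS or R, both already named. Follow-up is complete, so any variable whose test changes must be labelled post hoc and its new result shown beside the chi-square result. That display also covers the one real drawback, which is that Mann-Whitney would usually miss a difference in spread alone. The change does not remedy the low power that comes from 13 per arm.
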